## **Study outcomes:**

Acceptability of the intervention to users and HCP

- 1. Proportion of service users who attend the clinic that are scored by triage tool
- 2. Proportion of those who score high or medium who are offered the intervention
- 3. Proportion of those who are offered the intervention who take up the intervention
- 4. Proportion who take up the intervention who complete the intervention
- 6. Reasons for not completing the intervention from the qualitative study of participant

7. Acceptability of the intervention from the qualitative study of the staff

Feasibility and resource outcomes:

- 1. The total time spent by service users within the clinical service compared to normal
- 2. Total number of service users seen and STIs diagnosed, compared to normal
- 3. Average consultation time compared to normal
- 4. Number of patients seen by health advisors compared to normal
- 5. Extra HCP time required for the intervention
- Feasibility of active follow-up in an RCT
- 1. Proportion of service users who consented to the follow-up
- 2. Proportion of service users who were contactable at 3 months and complete the telephone interview
- 3. Proportion who had been for a STI screen or agreed to follow-up testing
- 4. Proportion of service users for whom there was a follow-up STI screen

**Data analysis/ sample size:** To investigate the feasibility of the intervention and understand the processes involved five measures will be collected: (i) the proportion of attendees triaged, among whom (ii) the proportion classified as medium or high risk, among whom (iii) the proportion offered the intervention, among whom (iv) the proportion that accept it, and among whom (v) the proportion who complete the intervention. All of these will be extracted from the EPR and calculated for each of the six centres implementing the intervention to see how this varies, and we will test for a difference in each between GUM clinics and Brook clinics by chi-squared test.

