The sample size is estimated from proportion (v) as this uses the smallest denominator. It also determines the number of participants who experienced the intervention. A total of 16000 patients attending the trial sites during the feasibility study period will be triaged leading to at least 400 completing the intervention (see figure 1), from among at least 800 accepting it, based on the above estimates. This sample size allows proportion (v) to be estimated with expected 95% confidence interval of 46 to 54%, and assuming 200 accept the intervention in Brook clinics and 600 at GUM. This provides over 80% power to detect a difference in completion such as 44 vs. 56% between these clinic types.

To investigate the feasibility of collecting the follow-up data envisaged for the main trial we will ask attendees whether they will agree to telephone follow-up. We will then, in a subsample of 400 from implementation site clinics and 300 from the control clinics, conduct telephone follow-up and calculate (i) the proportions opting for either a return visit to the clinic, or to be sent a kit for home sampling, and (ii) from among the two groups calculate the proportion completing follow-up (i.e. returning to clinic or returning a kit for testing). We will compare these proportions between GUM and Brook, and between clinics implementing the intervention and control, and between groups opting for a clinic appointment or home sampling. Analysis will use chi-squared test and logistic regression, to examine these differences jointly.

This sample size, if the overall follow-up is assumed to be around 60%, gives a 95% confidence interval of 56 to 64%. Assuming at least 150 select each follow-up method at intervention clinics and 120 at control clinics then we will have over 80% power to detect a difference of 53 vs. 67% in completed follow-up, and a difference of 54 vs. 66% between intervention and control clinics. Qualitative data will be analysed as in WP3

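### Completed follow-up is compared between clinic groups only among patients who chose a testing method, and the denominator of the assumed 60% overall follow-up is not stated

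*Protocol*

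**What the plan says.** The follow-up plan is in the Protocol, Work Package 5, under Study outcomes (Data analysis/ sample size). Telephone follow-up is to be done "in a subsample of 400 from implementation site clinics and 300 from the control clinics". Two measures follow. Measure (i) is the proportions choosing a return visit or a home sampling kit. For measure (ii), the plan will "from among the two groups calculate the proportion completing follow-up (i.e. returning to clinic or returning a kit for testing". These proportions are to be compared between GUM and Brook, "between clinics implementing the intervention and control, and between groups opting for a clinic appointment or home sampling", using chi-squared tests and logistic regression.

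The precision and power statements come next:

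- The sample size, "if the overall follow-up is assumed to be around 60%, gives a 95% confidence interval of 56 to 64" per cent.
- The power sentence opens with "Assuming at least 150 select each follow-up method at intervention clinics and 120 at control clinics".
- It then claims "over 80% power to detect a difference of 53 vs. 67% in completed follow-up", and also "a difference of 54 vs. 66% between intervention and control clinics".

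Just before this, the list headed Feasibility of active follow-up in an RCT gives four outcomes of equal rank: consent to follow-up; contact and a completed interview at 3 months; already screened or agreeing to testing; and "Proportion of service users for whom there was a follow-up STI screen". The last is worded per service user and is not limited to those who chose a method.

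**The concern.** Objective 8 asks whether a randomised trial of the package is feasible, and Work Package 6 expects such a trial to rely partly on active follow-up. The useful figure for that purpose is the share of patients selected for follow-up who end up with a test result. Measure (ii) is a later step: it describes people who were reached, interviewed and willing to pick a visit or a kit.

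Two problems follow. First, the only stated comparison of completed follow-up between intervention and control clinics is made in a group defined by a choice at the 3-month call, after the intervention. If the clinic groups differ in contact or willingness, that comparison can differ from the one over all selected patients in size or even direction. Second, the plan gives two denominators for completion (choosers in the analysis text, service users in the outcome list) and attaches neither to the 60%. Anyone planning the later trial from this figure could take it either way.

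**Working it through.** **Inputs** (Protocol, Work Package 5, Data analysis/ sample size). Subsample: 400 + 300 = 700. Minimum choosers: 2 × 150 = 300 of 400 (75%) at intervention clinics and, reading the 120 as per method too, 2 × 120 = 240 of 300 (80%) at control clinics. In total 540 of 700 (77.1%). Assumed follow-up: 60%. The significance level is not stated; two-sided 5% is assumed. Clustering by clinic is ignored throughout.

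**1. The plan's confidence interval**, as 0.60 ± 1.96 × √(0.60 × 0.40 / n):

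- n = 700: ± 3.63 points, 56.4 to 63.6%.
- n = 540: ± 4.13 points, 55.9 to 64.1%.

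Both round to the stated 56 to 64%, so the interval does not reveal the denominator.

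**2. The plan's power for 54 vs 66%**, by the normal approximation with pooled variance under the null: power = Φ{[|p1 − p2| − 1.96 √(p̄(1 − p̄)(1/n1 + 1/n2))] / √(p1(1 − p1)/n1 + p2(1 − p2)/n2)}.

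- Choosers, 300 vs 240: p̄ = 0.5933; (0.12 − 0.0834) / 0.0420 = 0.872; power 80.9% (78.3% with continuity correction).
- All selected, 400 vs 300: p̄ = 0.5914; (0.12 − 0.0736) / 0.0370 = 1.254; power 89.5% (88.0% with continuity correction).

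Without the correction, the stated power of over 80% is true of both. The chooser counts open the sentence and land just above 80%, which is suggestive but not conclusive.

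**3. The plan's power for 53 vs 67%**, read as clinic visit vs home kit: 270 vs 270 (both clinic groups pooled) gives 91.5%; 150 vs 150 gives 69.9%; 120 vs 120 gives 60.1%. The claim holds with the clinic groups pooled, at about 91%. The plan therefore also uses its over-80% wording for a power above 90%, which weakens any inference from step 2.

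**4. What the unstated denominator is worth.**

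- If 60% is the rate among 540 choosers: 0.60 × 540 = 324, and 324 / 700 = 46.3% (95% CI 42.6 to 50.0%).
- If 60% is the rate over all 700: 420 / 540 = 77.8% among choosers.

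The 540 is a minimum, so a range is needed:

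| Share choosing a method | Rate over all if 60% among choosers | Rate among choosers if 60% over all |
|---|---|---|
| 90% | 54% | 67% |
| 80% | 48% | 75% |
| 77.1% (stated minimum) | 46% | 78% |
| 70% | 42% | 86% |

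**5. What conditioning can do to the clinic comparison**, at the minimum shares (75% intervention, 80% control):

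- Equal 60% among choosers: 0.60 × 0.75 = 45% vs 0.60 × 0.80 = 48% over all selected.
- Equal 50% over all selected: 0.50 / 0.75 = 66.7% vs 0.50 / 0.80 = 62.5% among choosers.

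**6. Caution on the gain in power.** The rise from about 81% to about 89% is for the same 54 vs 66% on the larger denominators. A 54 vs 66% difference among choosers is a different quantity over all selected. At the minimum shares it becomes 40.5 vs 52.8% (power 90%) if intervention clinics are the lower group, but 49.5 vs 43.2% (power 38%) if they are the higher.

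**The case against.** The strongest answer is that the losses before the choice of method are in the plan. Measure (i) gives the share choosing, and the plan compares these proportions in the plural, so unequal choosing between clinic groups would be tested. Listed outcomes 2 and 3 report contact and agreement, and outcome 4 is already worded per service user. Multiplying (i) by (ii) recovers the rate over those telephoned. All of this stands. A reader might infer that the plan hides non-contact and refusal, or that (ii) is its principal follow-up measure. The documents support neither.

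A reader might also infer that the 60% is inflated. That is not shown either. It is called overall follow-up and comes directly after the 400 and 300, so 60% of 700 is a natural reading, and the interval fits both denominators. The 150 and 120 are lower bounds set for power, not forecasts, so 46% and 78% are the values at the stated minimum.

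Two further limits apply. The text does not say whether the 700 are people selected or people reached, and the follow-up flow chart, which may show this, is not reproduced in the copy reviewed. The two groups in measure (ii) could also be read as the intervention and control clinics, but the choice of visit or kit comes immediately before, and the bracketed explanation matches those two options.

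What the objection leaves untouched is that the stated comparison of completion uses choosers, and the per-service-user outcome is not named in the comparison or the power statement.

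**Conclusion.** The point holds in a limited form. On the plain reading, completed follow-up is calculated and compared between clinic groups only among patients who chose a visit or a kit, a choice made after the intervention. The outcome that avoids this is listed but not carried into the comparison, and the 60% has no stated denominator. At the plan's minimum of 540 choosers out of 700, that silence separates 60% from 46% in one direction and 60% from 78% in the other; the gap narrows as more patients choose a method. These sizes rest on reading the 120 as per method and treating the 700 as people selected. The documents do not establish that the follow-up rate is overstated: that would happen only if the rate among choosers were used as the follow-up rate for the later trial. This is an inexpensive improvement, not a fault that undermines the study.

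**What to change.** Make the proportion with a follow-up STI screen, among all patients selected for telephone follow-up (400 intervention, 300 control), the follow-up rate and the basis of the GUM-Brook and intervention-control comparisons. Count patients not reached, those refusing the interview and those declining both methods as not followed up. State that the 700 are patients selected, not patients reached, and say how those already screened since their appointment are counted, since listed outcome 3 includes them. Tie the 60% and its interval to this denominator, and restate the power for intervention vs control on 400 vs 300. Keep (i) and (ii) as descriptive steps, with (ii) used to compare clinic visit with home kit.

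The cost is wording and one further denominator from data already to be collected. The reported rate will be lower than the rate among choosers. If the 700 were meant as completed interviews, the number selected to reach them must also be recorded and used as the denominator.

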## **Project outputs**

1. Systematic review of brief sexual risk reduction interventions for high risk groups in a UK clinical setting.

2. A risk score algorithm adapted to SH-clinics and compatible with EPR systems to guide selection of intervention packages appropriate to particular health service users in accordance with their risk profile, and the service in which they are seen.

3. Development of an evidence-based tool kit of sexual risk reduction interventions, tailored to different high risk individuals.

4. Development of manuals for delivering the interventions in appropriate contexts (e.g., in clinic and at home) with fidelity strategies embedded.

5. An estimate of the feasibility of implementing the interventions in different clinical settings

6. Estimates of the cost of implementing the intervention package

7. Identification of a group of interested stakeholders, including service users (PPI), service providers (health advisors and service leads), other stakeholders (voluntary sector and commissioners) who can oversee the development of the next stage, e.g. RCT and the implementation and scale up of the intervention.

8. A trial design for a full evaluation and estimate of the feasibility of delivery of the trial

9. Plain English report for participants and service users.

10. Publications in peer-reviewed journals (to include feasibility/developmental work written up for publication).

11. Best Practice Guidelines for staff involved in delivering interventions

